6.3.1.2 TEAEs by System Organ Class and Preferred Term

The following summary tables of TEAEs will be provided by SOC and PT using frequency counts and percentages (i.e., number and percentage of participants with an event):

- All unsolicited TEAEs
- All unsolicited TEAEs that are treatment-related
- All unsolicited serious TEAEs
- All unsolicited serious TEAEs that are treatment-related
- All unsolicited TEAEs leading to discontinuation from participation in the study
- All unsolicited severe TEAEs
- All unsolicited severe TEAEs that are treatment-related
- All unsolicited treatment-emergent AESI

- All unsolicited medically attended TEAEs
- All unsolicited medically attended TEAEs that are treatment-related

6.3.1.2 TEAEs by Preferred Term

Summary tables of all unsolicited TEAEs within 28 days after vaccination will be provided. PTs will be sorted in a descending order according to the frequency in Total mRNA-1010 group.

6.3.1.3 TEAEs by System Organ Class, Preferred Term, and Severity/Toxicity

The following summary tables of TEAEs within 28 days after vaccination will be provided by SOC, PT, and maximum severity (mild, moderate, severe) or toxicity (Grade 1 through Grade 5) using frequency counts and percentages:

- All unsolicited TEAEs
- All unsolicited TEAEs that are treatment-related

6.3.2 Solicited Adverse Reactions

An AR is any AE for which there is a reasonable possibility that the IP caused the AE. The term “Solicited Adverse Reactions” refers to selected signs and symptoms occurring after injection administration during a specified post-injection follow-up period (day of injection and 6 subsequent days). The solicited ARs are recorded by the participant in the eDiary.

Any new safety information reported during safety telephone calls or at site visits (including a solicited reaction) that is not already captured in the eDiary will be described in the source documents as a verbally reported event. Any AR reported in this manner must be entered on the Reactogenicity eCRF and will be included in the evaluation of solicited ARs in addition to the eDiary data.

The occurrence and intensity of selected signs and symptoms are actively solicited from participants during a specified post-injection follow-up period (day of injection and 6 subsequent days), using a pre-defined checklist (i.e., solicited ARs). If a solicited local or systemic AR continues beyond 7 days post injection, the participant will be prompted daily to capture solicited local or systemic AR in the eDiary until no longer reported, not to exceed 28 days after vaccination.

The following local ARs will be solicited: injection site pain, injection site erythema (redness), injection site swelling/induration (hardness), and axillary (underarm) swelling or tenderness ipsilateral to the side of injection.

The following systemic ARs will be solicited: fever (an oral temperature greater than or equal to 38.0°C/100.4°F), headache, fatigue, myalgia (muscle aches all over the body), arthralgia (joint aches in several joints), nausea/vomiting, and chills.

The solicited ARs will be graded based on the grading scales presented in the protocol, modified from the Toxicity Grading Scale for Healthy Adult and Adolescent Volunteers Enrolled in Preventative Vaccine Clinical Trials (DHHS 2007). The investigator will assess Grade 4 (with exception of fever) solicited ARs recorded in eDiary or Reactogenicity CRF.

Analyses of solicited ARs will be provided by vaccination group (and then by age group) based on the Solicited Safety Set, unless otherwise specified. All solicited ARs (overall, local, and systemic) reported during the 7-day follow-up period after injection will be summarized. All solicited ARs will be considered causally related to injection.

The number and percentage of participants who reported each individual solicited local AR (has a severity grade of Grade 1 or greater) and solicited systemic AR (has a severity grade of Grade 1 or greater) during the 7-day follow-up period after injection or persisting beyond 7 days after injection will be tabulated by vaccination group and toxicity grade.

The number and percentage of participants who reported each individual solicited AR will also be summarized by vaccination group, toxicity grade, and day of reporting based on the eDiary and Reactogenicity CRF. Analyses will be displayed for each age group.

A two-sided 95% exact confidence interval (CI) using the Clopper-Pearson method will be provided for the percentage of participants who reported or any solicited AR, any solicited local AR, or any solicited systemic AR.

The onset of individual solicited AR is defined as the time point after injection at which the respective solicited AR first occurred. The number and percentage of participants with onset of individual solicited AR within 7 days will be summarized by vaccination group and onset day relative to injection day (Day 1). Analyses will be displayed for each age group.

The number of days reporting each solicited AR will be summarized descriptively and categorically for the following time windows (1-2 days, 3-4 days, 5-6 days, and ≥ 7 days) by vaccination group (and then by age group). The number of days will be calculated as

the day(s) the solicited AR is reported within 7 days of injection including the day of injection, no matter if it is intermittent or continued. If the solicited AR continues beyond 7 days, the days a solicited AR is reported after 7 days will be included (e.g., an event that lasted 5 days in the first 7 days post injection and 3 days beyond 7 days post injection, the duration will be reported as 8 (5 + 3) days). In addition, the duration for each solicited AR that started within 7 days of injection will be summarized descriptively. The duration of the solicited AR will be calculated as the last day – the first day + 1.

Solicited ARs collected in the eDiary and those collected in the reactogenicity eCRF will be provided in a listing, and the maximum toxicity grade from eDiary and reactogenicity eCRF will be presented. All solicited ARs that continue beyond 7 days post injection will be presented in separate data listings.

6.3.3 Clinical Laboratory Evaluations

Safety laboratory testing will include hematology and serum chemistry (Phase 1/2 only).

All laboratory test results will be presented in the data listings. The results that are outside the reference ranges will be flagged in the data listings. The abnormalities meeting the toxicity grading criteria (Grade 3 or higher) in [Appendix F](#) in any safety laboratory (hematology and serum chemistry) will be listed separately.

For continuous hematology and serum chemistry parameters, the observed values and changes from baseline will be summarized at each visit by vaccination group as defined in [Section 6.1](#). Hematology and chemistry toxicity grades will be summarized using a shift table from baseline to Day 8 by vaccination group.

A pregnancy test will be performed on all female participants of childbearing potential at the Screening Visit and before vaccine administration on Day 1 via point-of-care urine, and as needed at unscheduled visits (urine or blood pregnancy test based on the investigator's discretion). A follicle stimulating hormone (FSH) test may be performed at the Screening Visit (Day 0), as necessary and at the discretion of the investigator, to confirm postmenopausal status.

6.3.4 Vital Sign Measurements

Vital sign measurements, including systolic and diastolic blood pressures (BP), heart rate, respiratory rate, and body temperature, will be presented in a data listing. The values that are outside the reference ranges will be flagged in the data listing. The abnormalities

meeting the toxicity grading criteria (Grade 3 or higher) in [Appendix G](#) in any vital sign measurement will be listed separately.

Observed values and changes from pre-injection to post-injection at Day 1 for all vital sign measurements will be summarized by vaccination group as defined in [Section 6.1](#). Shift from baseline in the toxicity grades to post-injection result at Day 1 will also be summarized by vaccination group.

6.4 Immunogenicity Analysis

The following description of immunogenicity analyses will be applied to Phase 1/2, Phase 2 NH, and Phase 2 Extension. Phase 2 NH and Phase 2 Extension will share the same analyses, unless otherwise specified.

The analyses of immunogenicity will be based on the PP Set and will be performed by vaccination group as defined in [Section 6.1](#). If the number of participants in the FAS and PP Set differs (defined as the difference divided by the total number of participants in the PP Set) by more than 10% for each age group, supportive analyses of immunogenicity may be conducted using the FAS. The supportive analysis is required if the condition is met.

The GMT and geometric mean (GM) level will be calculated using the following formula:

$$2^{\left\{ \frac{\sum_{i=1}^n \log_2(t_i)}{n} \right\}}$$

where t_1, t_2, \dots, t_n are n observed immunogenicity titers or levels.

The GMFR measures the changes in immunogenicity titers or levels within participants. The GMFR will be calculated using the following formula:

$$2^{\left\{ \frac{\sum_{i=1}^n \log_2(v_{ij}/v_{ik})}{n} \right\}} = 2^{\left\{ \frac{\sum_{i=1}^n \log_2(v_{ij}) - \log_2(v_{ik})}{n} \right\}}$$

where, for n participants, v_{ij} and v_{ik} are observed immunogenicity titers or levels for participant i at time points j and k , $j \neq k$.

The 95% CIs for GMT and GMFR will be calculated based on the t distribution of the log-transformed values then back transformed to the original scale for presentation, unless otherwise specified.

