An analysis of covariance model will be carried out with HAI titers at Day 29 as a dependent variable and a group variable as the fixed variable. The GMT of the mRNA-1010 at Day 29 will be estimated by the geometric least square mean (GLSM) from the model. The geometric mean ratio (GMTr; ratio of GMT) will be estimated by the ratio of GLSM from the model. The corresponding 2-sided 95% CI will be provided to assess the difference in immune response between the mRNA-1010 compared with the active comparator at Day 29.

The number and percentage of participants with seroconversion due to vaccination will be provided with 2-sided 95% CI using the Clopper-Pearson method at Day 29. The seroconversion rate difference with 95% CI at Day 29 will be provided.

In addition, the GMT of HAI titers with corresponding 95% CI will be provided at each time point. The 95% CIs will be calculated based on the t-distribution of the log 2-transformed values and then back transformed to the original scale. The GMFR of HAI titers with corresponding 95% CI at each postbaseline time point over baseline will be provided. Descriptive summary statistics, including median, minimum, and maximum, will also be provided.

For summarizations of GMTs, antibody titers reported as LLOQ will be replaced by $0.5 \times$ LLOQ. Values that are greater than ULOQ will be converted to the ULOQ.

Rate of seroconversion is defined as (1) if LLOQ is 1:10, the proportion of participants with either a prevaccination HAI titer $<$ 1:10 and a postvaccination HAI titer \geq 1:40 or a prevaccination HAI titer \geq 1:10 and a minimum 4-fold rise in the postvaccination HAI antibody titer; or (2) if LLOQ is greater than 1:10, the proportion of participants with either a prevaccination HAI titer $<$ LLOQ and a postvaccination HAI \geq 4 times of LLOQ, or a prevaccination HAI \geq LLOQ and a minimum 4-fold rise in the postvaccination HAI .

The HAI titers at Day 29, GMTr at Day 29, and the difference in seroconversion rate at Day 29 may also be performed with the Full Analysis Set as supplementary analyses.

Phase 2 Extension

Immune responses, as measured by GMT and seroconversion rate in the mRNA-1010 groups based on Day 29 HAI titers, will be compared with that of participants receiving active comparator for all 4 strains.

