IST	internal safety team
LLOQ	lower limit of quantification
MAAE	medically attended adverse event
max	maximum
MedDRA	Medical Dictionary for Regulatory Activities
min	minimum
MN	microneutralization
mRNA	messenger ribonucleic acid
NH	Northern Hemisphere

Abbreviation	Definition
NP	nasopharyngeal
PP	per-protocol
PT	preferred term
RT-PCR	reverse transcriptase polymerase chain reaction
SAE	serious adverse event
SAP	statistical analysis plan
SAS	Statistical Analysis System
SD	standard deviation
SoE	schedule of events
SOC	system organ class
TEAE	treatment-emergent adverse event
ULOQ	upper limit of quantification
WHO	World Health Organization
WHODrug Global	World Health Organization drug dictionary

1 Introduction

This statistical analysis plan (SAP), which describes the planned analyses for Study mRNA-1010-P101, is based on the most recent approved clinical study protocol (CSP), Amendment 4, dated 03-Feb-2022, and the most recent approved electronic case report form (eCRF), dated 01-Mar-2022.

In addition to the information presented in the statistical analysis plan section of the protocol (Section 9), which provides the principal features of analyses for this study, this SAP provides statistical analysis details/data derivations. It also documents modifications or additions to the analysis plan that are not “principal” in nature and result from information that was not available at the time of protocol finalization.

Study mRNA-1010-P101 is a Phase 1/2, randomized, stratified, observer-blind, dose-ranging study to evaluate the safety, reactogenicity, and immunogenicity of messenger ribonucleic acid (mRNA)-1010 seasonal influenza vaccine in healthy adults 18 years and older. Study design and analyses for Phase 1/2, and Phase 2 Northern Hemisphere, and Phase 2 Extension parts of the study will be described separately in the SAP, unless otherwise specified.

PPD Biostatistics and Programming team, designee of Moderna Biostatistics and Programming department, will perform the statistical analysis of the safety, reactogenicity, and immunogenicity data; Statistical Analysis System (SAS) Version 9.4 or higher will be used to generate all statistical outputs (tables, figures, listings, and datasets). The SAP will be finalized and approved prior to the primary analysis clinical database lock and treatment unblinding for the study. If the methods in this SAP differ from the methods described in the protocol, the SAP will prevail.

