4.4.3 Phase 2 Extension

Approximately 200 participants will be randomly assigned in a 1:1:1:1 ratio to receive either mRNA-1010 6.25 µg, mRNA-1010 12.5 µg, mRNA-1010 25 µg, or licensed quadrivalent seasonal influenza vaccine (active comparator), with approximately 50 participants randomly assigned to each mRNA-1010 vaccination group and 50 participants to the Active Comparator Group. Randomization will be stratified by age (18 to < 50 years or ≥ 50 years), with at least 30% of participants in each dose group being ≥ 50 years of age.

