6.1 General Considerations

For Phase 1/2, Phase 2 NH, and Phase 2 Extension, the Schedules of Events (SoE) are provided in [Appendix E](#).

General considerations for analyses will be applied to Phase 1/2, Phase 2 NH, and Phase 2 Extension, unless otherwise specified. All analyses will be conducted using SAS Version 9.4 or higher. Statistical outputs (tables, figures, listings, and datasets) will refer study participants as subjects and will use injection of IP and injection interchangeably.

For the summary statistics of all numerical variables unless otherwise specified, the display precision will follow programming standards. Please see [Appendix A](#) for variable display standards.

When count data are presented, the percentage will be suppressed when the count is zero in order to draw attention to the non-zero counts. A row denoted “Missing” will be included in count tabulations where specified on the shells to account for dropouts and missing values. The denominator for all percentages will be the number of participants in that vaccination group within the analysis set of interest, unless otherwise specified.

Continuous variables will be summarized using the following descriptive summary statistics: the number of participants (n), mean, standard deviation (SD), median, minimum (min), and maximum (max).

Categorical variables will be summarized using counts and percentages.

Baseline value is defined as the most recent non-missing measurement (scheduled or unscheduled) collected before injection, unless otherwise specified. For immunogenicity tests and nasopharyngeal (NP) swab tests, the baseline is defined as the most recent non-missing result/measurement (scheduled or unscheduled) collected before or on the date (and time, if available) of injection (Day 1).

Study day relative to injection will be calculated as below:

- Study day prior to injection will be calculated as: date of assessment/event – date of injection.
- Study day on or after the date of injection will be calculated as: date of assessment/event – date of injection + 1.

For calculation regarding antibody levels/titers, antibody values reported as below lower limit of quantification (LLOQ) will be replaced by $0.5 \times \text{LLOQ}$. Values that are greater than the upper limit of quantification (ULOQ) will be converted to the ULOQ. Missing results will not be imputed.

The following **analysis periods for safety analyses** will be used in this study:

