6.1.2 Phase 2 Northern Hemisphere

Age groups:

The following age groups will be used for summary purposes:

- Overall
- Age: ≥ 18 to < 50 years
- Age ≥ 50 to < 65 years
- Age ≥ 65 years

Vaccination status:

The following previous flu vaccination status may be used for summary purposes:

- Received season flu vaccine in the previous season
- Not received season flu vaccine in the previous season

Vaccination groups:

The following vaccination groups will be used for summary purposes:

- mRNA-1010 25 µg
- mRNA-1010 50 µg
- mRNA-1010 100 µg
- Active comparator

For Phase 2 NH, all analyses and data summaries/displays will be provided by vaccination group (and then by age group) using appropriate analysis population, unless otherwise specified. Summaries may also contain a display for all mRNA-1010 vaccination groups (Total mRNA-1010 group) or all vaccination groups, including active comparator (Overall group). Additional summaries/displays based on vaccination status will be provided for immunogenicity analyses only.

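### The trigger that makes the supportive FAS immunogenicity analysis mandatory (SAP 6.4) is set by age group, not by vaccination group, so PP exclusions concentrated in one arm need not set it off

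*SAP*

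**What the plan says.** - **Trigger.** SAP 6.4 bases immunogenicity on the PP Set, by vaccination group. If FAS and PP counts differ "by more than 10% for each age group, supportive analyses of immunogenicity may be conducted using the FAS". The difference is "defined as the difference divided by the total number of participants in the PP Set".
- **Status.** The next sentence reads "The supportive analysis is required if the condition is met". The same condition is therefore described first as permissive and then as binding.
- **Primary contrasts.** SAP 6.4.3.1 compares each mRNA-1010 group with the active comparator at Day 29, by GMT ratio and by seroconversion difference.
- **PP exclusions.** SAP 5.3 removes participants for dosing error (with cut-offs that depend on the assigned arm), sampling outside the window, PCR-documented influenza through Day 29, and major deviations that affect the immune response.
- **Protocol provision.** The protocol synopsis, under the joint Phase 2 NH and Phase 2 Extension text, says the Day 29 titer, GMT ratio and seroconversion-difference analyses "may also be performed with the Full Analysis Set as supplementary analyses". Protocol 9.5.3 repeats this under Phase 2 NH.

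**The concern.** All the PP exclusions arise after randomisation. Exclusions that fall evenly across arms are less of a worry for a between-arm contrast. Exclusions that differ between arms are what can distort the GMT ratio and the seroconversion difference. A check on PP depletion should therefore look at arms, and the one in SAP 6.4 names only age groups.

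Uneven exclusion is plausible. Dosing-error rules differ by arm, and Phase 2 NH vaccinates during the influenza season, so infection before Day 29 could differ by arm. At stake is a descriptive comparison on a primary objective, reported from an unevenly depleted PP Set with no compulsory FAS result beside it.

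**Working it through.** The 10% threshold is a rule, so there is no planned figure to reproduce. The check applies the SAP's own metric, with x = FAS count minus PP count and N = FAS count:

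ratio = x / (N − x), trigger if above 10%.

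**Inputs from the documents.** Extension: about 200 participants, 50 per arm, "with at least 30% of participants in each dose group being ≥ 50 years of age" (SAP 4.4.3). NH: about 500, as 150/150/150/50 (SAP Table 1).

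**Assumptions.** Everyone randomised is dosed. Ten of 50 are excluded in one arm and none elsewhere. The documents give no expected exclusion rate. Extension age split: 35/15 per arm, 140/60 overall (the 30% minimum), with 25/25 per arm, 100/100 overall, as the other end of the range.

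**1. Extension, arms pooled within age group**

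| Overall split | Exclusions, 18 to <50 / ≥50 | 18 to <50 | ≥50 | *Any* | *Every* |
|---|---|---|---|---|---|
| 140/60 | 7/3 | 7/133 = 5.3% | 3/57 = 5.3% | no | no |
| 140/60 | 5/5 | 5/135 = 3.7% | 5/55 = 9.1% | no | no |
| 140/60 | 4/6 | 4/136 = 2.9% | 6/54 = 11.1% | fires | no |
| 100/100 | 5/5 | 5/95 = 5.3% | 5/95 = 5.3% | no | no |
| 100/100 | 10/0 | 10/90 = 11.1% | 0/100 = 0% | fires | no |

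Pooled over age as well, the ratio is 10/190 = 5.3%. Within the affected arm it is 10/40 = 25% in every row. With 140/60, the *any* reading fires only if at least 6 of the 10 are aged 50 or older.

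**2. Extension, read arm by arm (35/15)**

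- Arm overall: 10/40 = 25%, fires.
- Split 7/3: 7/28 = 25% and 3/12 = 25%, fires under *any* and *every*.
- All 10 aged 18 to <50: 10/25 = 40% and 0/15 = 0%. *Any* fires; *every* does not.

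**3. NH comparator**

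Pooled over arms and age: 10/490 = 2.0%, against 10/40 = 25% within the arm. This shows how 3:3:3:1 allocation dilutes a problem in the smallest arm. It does not settle whether the rule fires, because the NH age-group sizes are not given. If 100 participants were aged 65 or older and all 10 exclusions fell there, that group would reach 10/90 = 11.1% and *any* would fire.

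**4. A trigger set on the arm**

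- Arm of 50: 4/46 = 8.7%, no; 5/45 = 11.1%, fires.
- Arm of 150: 13/137 = 9.5%, no; 14/136 = 10.3%, fires.

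**The case against.** **The rule can be read arm-wise.** SAP 6.1 states: "The denominator for all percentages will be the number of participants in that vaccination group within the analysis set of interest, unless otherwise specified". SAP 6.1.2 presents analyses "by vaccination group (and then by age group) using appropriate analysis population", and SAP 6.4 itself speaks of analysis by vaccination group just before the trigger. This stands as an open reading, and under it the 25% arm fires overall. But the trigger's divisor is stated as the total PP count with no mention of arm, so pooling is the more natural reading. Even arm-wise, *any* versus *every* is unresolved.

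**The FAS analysis is already available.** This stands. A reader might infer that the SAP threshold displaces the protocol's permission, because SAP 1 says "If the methods in this SAP differ from the methods described in the protocol, the SAP will prevail". The documents do not support that. SAP 6.4 says when the run becomes required and does not forbid it otherwise, and SAP 7 records no changes from the protocol's planned analyses. The protocol's permission holds at any exclusion rate, but it remains optional.

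**The imbalance would be visible.** SAP 6.2.1 tabulates set membership by arm and age and summarises PP-exclusion reasons. SAP 6.2.2 gives demographics on both FAS and PP. The primary model also adjusts for baseline titer and age group, plus prior vaccination status in NH. All this helps, but seeing an imbalance does not show its effect on the estimates.

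**The remedy has limited reach.** Missing titers are not imputed (SAP 6.1), so the FAS restores only participants with a Day 29 titer and, for the adjusted model and seroconversion, a baseline titer. Those restored may be out of window, misdosed or infected. This stands, and it makes the FAS run a sensitivity check only.

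**Conclusion.** The point holds in a bounded form. With arms pooled within age group, exclusions concentrated in one arm need not make the FAS check mandatory: a 25% difference in one Extension arm can appear as 5.3% in both age groups. The same failure is possible arm-wise if every age group must exceed 10%.

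A reader might go further and conclude that the rule would certainly miss a depleted NH comparator arm, or that the PP results will be biased. Neither follows. The NH figure is pooled over age while the rule tests age groups, and some age distributions would fire it. No exclusion rate is given, so the counts here are illustrations, not forecasts. A difference between FAS and PP results would not by itself prove PP bias.

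The comparisons are descriptive (protocol 9.2 and SAP 4.2 test no hypothesis) and the FAS run is supportive, so this is a low-to-moderate priority. It is still worth correcting, because the trigger does not address the contrast it is meant to protect.

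**What to change.** In SAP 6.4, for Phase 2 NH and Phase 2 Extension, run the Day 29 GMT ratio and seroconversion difference on the FAS as a supportive analysis regardless of the threshold.

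At minimum, require it when the FAS–PP difference exceeds 10% of the PP count in any vaccination group. If the age-group condition is kept, state whether any or every age group must exceed 10%, and whether arms are pooled. In either case, reconcile the permissive and mandatory sentences.

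The cost is re-running existing table programs on a second analysis set and some extra tables. The report should say that the FAS analyses participants as randomised and includes misdosed and infected participants, so readers treat it as a sensitivity check.
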